3.24.	Continuance	For the subject to continue in the study, they must meet both of the following criteria: 
 
• Visual acuity is 20/30 or better OD and OS
 
• Subject willing to use the drop at least 3x a day for 7-9 days.
 
	
3.25.	Dispense	The artificial tears will be dispensed for a 7-9 day wearing period 
 
• Dispense enough artificial tears to last the whole week.
 
• A patient instruction guide will be provided.
 
 Subjects will be scheduled for Visit 4 in approximately 7-9 days.	Dispense

#### VISIT 4

The subjects must present to visit 4 wearing their habitual spectacles (if applicable) having used the study drop in both eyes at least 2 times that day.

Visit 4: Follow-up of Drop #2			
Step	Procedure	Details	
4.1.	Adverse Events and Concomitant Medications Review	Review any changes to the subject's medical history or concomitant medications from the previous study visit. Record any changes, and any adverse events.	
4.2.	Artificial Tear Use	The subject will be asked about their artificial tear use.	
4.3.	Collection of Study drops	The site will collect and discard the bottle of study eye drops.	

Visit 4: Follow-up of Drop #2			
Step	Procedure	Details	
4.4.	Subject Reported Ocular Symptoms	Subjects will respond to a verbal open-ended symptoms questionnaire.	██████████
4.5.	Modified DEQ-5 Questionnaires	The subject will respond to the modified DEQ-5 Questionnaires.	██████████ Appendix A
4.6.	OSDI Questionnaire	The subject will respond to the OSDI questionnaire.	██████████ Appendix A
4.7.	VAS Questionnaire	The subject will respond to the VAS comfort questionnaire	██████████
4.8.	Visual Acuity	Record the distance high contrast visual acuity to the nearest letter (OD, OS, and OU) with their habitual spectacle correction in place (or unaided if applicable).	Eurolens Research SOP ██████████
4.9.	Tear film lipid layer thickness	Record the tear film lipid layer thickness, OD & OS	Measure per LipiView II® II manufacturer instruction (Appendix D)
4.10.	Habitual tear film stability (Medmont)	Record the tear film stability (NITBUT), OD & OS	NITBUT Medmont Work Aid (Appendix E)
4.11.	Slit Lamp Biomicroscopy	The FDA slit lamp classification scale will be used to grade the findings.  (All ocular AE's must be followed to resolution)  If the clearance of the fluorescein needs to be expedited, preservative-free rewetting drops or saline may be instilled.	██████████
4.12.	Expanded Sodium Fluorescein Corneal Staining	Corneal Staining Assessment (1.0 scale units) will be assessed using a more detailed scale for internal purposes only.	██████████

## FINAL EVALUATION

The final evaluation will ordinarily take place immediately following the last scheduled follow-up visit per the study protocol. It may also take place at any point the subject discontinues the study or is terminated from the study.

Final Evaluation			
Step	Procedure	Details	████
F.1	Final Exam Form	Indicate if the subject completed the study successfully. If subject discontinued from the study indicate the reason.	
F.2	Exit Distance Visual Acuity	Record the exit distance visual acuity OD, OS, OU with the subject's spectacles or unaided (the same method as used in Visit 1 Baseline entrance distance visual acuity).	EuroLens Research SOP █████

### 7.3. Unscheduled Visits

If, during the investigation, a subject requires an unscheduled visit to the clinical site, the following information will be collected at a minimum:

- Chief complaint prompting the visit. If the reason is an adverse event, the applicable eCRF for the adverse event must be completed and subject record completed as appropriate
- Date and time of the visit and all procedures completed at the unscheduled visit
- Review of adverse event and concomitant medications
- Documentation of any test article dispensed or collected from the subject, if applicable
- Slit lamp findings (using the Slit Lamp Classification Scale)

If the Investigator withdraws a subject from the study, the final study visit case report forms must be completed indicating the reason(s) why the subject was withdrawn. The subject record must be completed documenting the date and primary reason for withdrawal and the study CRA notified.

Any ocular and non-ocular adverse events that are ongoing at the time of the study visit will be followed by the Investigator, within licensure, until they have resolved, returned to pre-treatment status, stabilized, or been satisfactorily explained. If further treatment i.e., beyond licensure is required, the subject will be referred to the appropriate health care provider.

The following information will be collected during an unscheduled visit (when applicable)

Unscheduled Visit			
Step	Procedure	Details	████
U.1	Chief Complaints	Record the subject's chief complaints for reasons for the unscheduled visit.	
U.2	Adverse Events and Concomitant Medications Review	Review any changes to the subject's medical history or concomitant medications	

Unscheduled Visit			
Step	Procedure	Details	
		from the previous study visit. Record any changes, and any adverse events.	
U.3	Entrance VA	Record the distance high contrast visual acuity to the nearest letter (OD, OS, and OU) with their habitual spectacle correction in place (or unaided if applicable).	Eurolens Research SOP [REDACTED]
U.4	Dispensing	Dispensing of additional artificial tear drops, if necessary	
U.5	Slit Lamp Biomicroscopy	The FDA slit lamp classification scale will be used to grade the findings.  (All ocular AE's must be followed to resolution)  If the clearance of the fluorescein needs to be expedited, preservative-free rewetting drops may be instilled.	[REDACTED]
U.6	Exit Visual Acuity	Record the distance high contrast visual acuity to the nearest letter (OD, OS, and OU) with their habitual spectacle correction in place (or unaided if applicable).	Eurolens Research SOP [REDACTED]

#### 7.4. Laboratory Procedures

Not applicable.

### 8. SUBJECTS COMPLETION/WITHDRAWAL

#### 8.1. Completion Criteria

Subjects are considered to have completed the study if they:

- Provided informed consent;
- They are eligible;
- Completed all study visits;
- Have not withdrawn/discontinued from the study for any reason described in Section 8.2

#### 8.2. Withdrawal/Discontinuation from the Study

A subject will be withdrawn from the study for any of the following reasons:

- Subject death during the study period
- Subject withdrawal of consent
- Subject not compliant to the study protocol including drop usage schedule
- Subject lost to follow-up
- Subject no longer meets eligibility criteria (e.g. the subject becomes pregnant)
- Subject develops significant or serious adverse events causing discontinuation of study drop
- Subjects who have experienced a Corneal Infiltrative Event (CIE)

- Investigator's clinical judgment regarding the subject safety reasons (that it is in the best interest of the subject to stop treatment)
- Subject not successfully dispensed due to lack of efficacy or safety

For discontinued subjects, the Investigator will:

- Complete the current visit (scheduled or unscheduled)
- Complete the Final Evaluation, indicating the reason that the subject was discontinued from the study
- Collect used test article(s) (brought to the visit) from the subject and discard them, unless otherwise stated in Section 7.2
- Collect all unused test article(s) from the subject

An additional subject may be enrolled if a subject discontinues from the study prematurely.

In cases where a subject is lost to follow-up, every possible effort must be made to contact the subject and determine the reason for discontinuation/withdrawal. The measures taken to follow up must be documented including two written attempts and a certified letter (or equivalent) as the final attempt.

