## **4. STUDY DESIGN AND RATIONALE**

### **4.1. Description of Study Design**

The study design is a randomized, double-masked, bilateral, 2 treatment × 2 period, dispensing, 4-visit study.

After a pre-screening assessment, eligible subjects will be invited to attend an initial visit. At study Visit 1, subjects will be consented and screened for inclusion/exclusion criteria. If a subject is found to meet all eligibility criteria, they will be dispensed with the first artificial tears eye drops based on the randomization scheme; otherwise, the subject will be discontinued from the study. After dispensing of the first eye drop solution; NITBUT, LipiView II® measurement at taken at approximately 5 mins, 30 mins, 1 hour, and 2 hours post drop

Subjects will be dispensed with their randomly assigned eye drops and instructed to use them OU at least 3 times a day over a 7-9 day period. The follow-up evaluation (Visit 2) will occur 7-9 days after the initial visit. At this visit questionnaires, LipiView II®, NITBUT, slit lamp findings will be captured.

After completion of Visit 2, there is a 7-9 day washout period during which subjects may use their habitual products, if any, but they will be advised not use any eye drops on the day of Visit 3

Following the washout period, the subject returns for Visit 3 and is dispensed with the second randomized eye drop with NITBUT, LipiView II® measurements at approximately 5 mins, 30 mins, 1 hour, and 2 hours post drop. Subjects will be dispensed with their second randomly assigned eye drops and instructed to use them OU at least 3 times a day over a 7-9 day period. Visit 4 takes place 7-9 days after visit 3, at which questionnaires, LipiView II®, NITBUT, slit lamp findings, final evaluation will take place.

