1.24	VAS Questionnaire	The subject will respond to the VAS comfort questionnaire	
1.25	Tear film lipid layer thickness- 120 minutes	Record the tear film lipid layer thickness, OD & OS	Measure per LipiView II® II manufacturer instruction (Appendix D)
1.26	VAS Questionnaire	The subject will respond to the VAS comfort questionnaire	
1.27	Exit Visual Acuity	Record the distance high contrast visual acuity to the nearest letter (OD, OS, and OU) with their habitual spectacle correction in place (or unaided if applicable).	Eurolens Research SOP
1.28	Continuance	For the subject to continue in the study, they must meet both of the following criteria: 
 
• Visual acuity is 20/30 (0.18logMAR) or better OD and OS
 
• Subject willing to use the drop at least 3x a day OU for 7-9 days.
 
	
1.29	Instillation of drops training	Instruct and teach instillation of drops.	
1.30	Dispense	The artificial tears will be dispensed for a 7-9 day wearing period 
 
• Dispense enough artificial tears to last the whole week.
 
• A patient instruction guide will be provided.
 
• Subjects will be scheduled for Visit 2 in approximately 7-9 days.
 
	

## VISIT 2

The subjects must present to visit 2 wearing their habitual spectacles (if applicable) having used the study drop in both eyes at least 2 times that day.

Visit 2: Follow-up on drop #1			
Step	Procedure	Details	
2.1.	Adverse Events and Concomitant Medications Review	Review any changes to the subject's medical history or concomitant medications from the previous study visit. Record any changes, and any adverse events.	

Visit 2: Follow-up on drop #1			
Step	Procedure	Details	
2.2.	Artificial Tear Use	The subject will be asked about their artificial tear use.	
2.3.	Collection of Study drops	The site will collect and discard the bottle of study eye drops.	
2.4.	Subject Reported Ocular Symptoms	Subjects will respond to a verbal open-ended symptoms questionnaire.	
2.5.	DEQ-5 Questionnaires	The subject will respond to the DEQ-5 Questionnaires.	Appendix A
2.6.	OSDI questionnaire	The subject will respond to the OSDI questionnaire.	Appendix A
2.7.	VAS Questionnaire	The subject will respond to the VAS comfort questionnaire	
2.8.	Visual Acuity	Record the distance high contrast visual acuity to the nearest letter (OD, OS, and OU) with their habitual spectacle correction in place (or unaided if applicable).	Eurolens Research SOP

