#### **Intent-to-Treat (ITT) Population:**

All randomized subjects regardless of actual treatment and subsequent withdrawal from study or deviation from protocol. At least one observation should be recorded.

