#### **14.9. Procedure for Handling Missing Data and Drop-Outs**

Missing or spurious values will not be imputed. The count of missing values will be included in the summary tables and listings.

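### Mandatory withdrawal for missing the drop schedule ends outcome collection early: it costs mainly period-2 data and precision, with a risk of bias only under specific conditions

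*Combined protocol and SAP*

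**What the plan says.** - **Withdrawal rule, Section 8.2.** The list opens "A subject will be withdrawn from the study for any of the following reasons" and includes "Subject not compliant to the study protocol including drop usage schedule". No number of missed doses or days is given. The schedule itself is in Section 4.1, where subjects are "instructed to use them OU at least 3 times a day over a 7-9 day period".
- **After discontinuation, Section 8.2.** The investigator finishes the visit in progress, scheduled or not, and then the Final Evaluation. The Final Evaluation table in Section 7.2 holds a completion form and exit visual acuity, with no VAS or OSDI. No later scheduled visit is provided for.
- **Order within visits, Section 7.2.** At Visit 2, step 2.2 reads "The subject will be asked about their artificial tear use"; OSDI follows at 2.6 and VAS at 2.7. Visit 4 keeps that order (4.2, 4.6, 4.7).
- **Unscheduled visits, Section 7.3.** The minimum list and the step table contain neither VAS nor OSDI.
- **Populations, Section 14.3.** ITT is "All randomized subjects regardless of actual treatment and subsequent withdrawal from study or deviation from protocol", followed by "At least one observation should be recorded". A separate per-protocol set removes non-completers and substantial deviators.
- **Analysis, Sections 14.5 and 14.9.** The primary model is a bivariate Bayesian model over the two periods with an unstructured covariance matrix. No analysis population is named, and nothing says how a subject with one period outcome enters. On missing data: "Missing or spurious values will not be imputed".

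**The concern.** Section 4.2 chose the crossover because each subject serves as their own control. Withdrawal between the periods removes exactly that contrast. Non-compliance does not need withdrawal to be dealt with analytically: Section 10 already has deviations reported and tracked, and the per-protocol set already removes the substantial ones.

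The reason for non-compliance may also matter. The primary endpoint is comfort, and Section 1.4 lists burning, stinging and reduced comfort as known risks of artificial tears. Skipping doses because a drop is uncomfortable is a plausible route, and it would tie the missing data to the outcome. At stake are some precision and, depending on analysis choices the plan leaves open, the direction of the estimate.

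**Working it through.** **1. What is lost, by when non-compliance is found** (Sections 7.2, 7.3 and 8.2 read together)

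| Found at | Outcomes kept | Outcomes lost |
|---|---|---|
| Visit 2 | Period 1 VAS and OSDI | Visit 4 VAS and OSDI, hence the contrast |
| Visit 4 | Both periods | None |
| Unscheduled contact, period 1 | None assured | Possibly period 1, and period 2 |
| Unscheduled contact, period 2 | Period 1 | Possibly period 2 |

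Table 3 schedules no contact between Visits 1 and 2 or between Visits 3 and 4, so the last two rows are the exception.

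**2. Reproducing Table 4.** Inputs from Section 14.2: differences 5 and 10; correlations 0.30, 0.50 and 0.80; paired test; 50 completers. A two-sided 5% test is assumed. SD of the difference = SD × √(2(1 − ρ)); noncentrality = Δ√n / SD of the difference; power from the noncentral t on n − 1 degrees of freedom.

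- With SD 25, all six cells match: 21.6, 28.4, 59.2, 64.9, 79.2 and 99.2%.
- The text gives a variance of 25. That is SD 5, which gives about 100% in every cell, so SD 25 is used here.

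**3. Precision.** At Δ = 10 and ρ = 0.5, the SD of the difference is 25 × √1 = 25.

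| Complete pairs | Noncentrality 10√n/25 | Power |
|---|---|---|
| 40 | 2.53 | 69.4% |
| 45 | 2.68 | 74.7% |
| 50 (planned) | 2.83 | 79.2% |
| 55 | 2.97 | 83.0% |
| 60 (no loss) | 3.10 | 86.2% |

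The documents give no non-compliance rate. Saving 5 of the 10 allowed losses is an illustration; 40 to 60 pairs is an assumed range.

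**4. Bias.** Simulation under assumed mechanisms: 60 subjects, SD 25, mean comfort 60, ρ = 0.5, true Test-Control difference 5, no period effect, 1,500 trials. A likelihood model with known covariance stands in for the Bayesian model. The basic non-compliance probability is 15% per period on either drop, or 30% if on Test only. Entries are mean estimates: available-data likelihood / complete pairs only.

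| Cause of non-compliance | (a) Current-visit VAS kept | (b) Own-period VAS also lost |
|---|---|---|
| Random, either drop | 5.02 / 5.04 | 5.04 / 5.07 |
| Test only, unrelated to comfort | 4.91 / 4.89 | 5.15 / 5.16 |
| Low comfort, either drop | 4.98 / 4.80 | 4.78 / 4.84 |
| Low comfort, Test only | 5.08 / 7.14 | 10.36 / 9.29 |

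Incomplete pairs are 15–18% under (a) and 28–31% under (b). Simulation error is about 0.1 (for example 3.48/√1500 = 0.09).

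With a true difference of 0, the last mechanism, and ρ from 0.3 to 0.8:

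- Likelihood bias is 0.0 under (a) and falls from 7.5 to 2.6 under (b).
- Complete-pairs bias falls from 3.3 to 1.0 under (a) and from 6.5 to 1.9 under (b).

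**The case against.** **The ITT definition is not breached.** A reader might infer that Section 8.2 removes outcomes that the ITT definition undertakes to keep. It does not. The definition foresees withdrawal and asks for one recorded observation; it does not promise both periods. Section 14.5 also never makes ITT the primary set. This stands. What remains is a poor fit between the rules, not a contradiction.

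**The loss is narrower than it looks.** Finishing the visit in progress keeps the week-1 VAS of the non-compliant period when the problem surfaces at Visit 2 or 4. This stands as well.

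**Treatment-related loss is not documented.** A reader might infer that the loss favours Test. No passage gives non-compliance by drop, and in the simulation loss that differed by drop but not by comfort left the estimate near 5.

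**Completer means overstate the bias.** Suppose 5–15% are withdrawn with Test-Control differences of −10 to −20. The formula (D − w·Dw)/(1 − w) then gives +0.5 to +3.5 for a true 0 and 11.1 to 15.3 for a true 10. It counts subjects taking Test second and found at Visit 4, who lose nothing. If both sequences are equally affected, w halves to 2.5–7.5% and the ranges become +0.3 to +1.6 and 10.5 to 12.4. Even these describe complete pairs, and the planned model is not restricted to them.

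**Precision is partly provided for.** Fifty completers is the target, replacement is allowed, the sample size was not based on a power calculation, and Section 2.3 calls the hypotheses exploratory. This limits the weight of the point, but none of it addresses selective loss.

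**Continued collection helps only if the second drop is dispensed.** True: otherwise the Visit 4 score carries no contrast. The gain is confined to subjects who go on to the second drop.

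**Conclusion.** The point holds in limited form. As written, missing the drop schedule by any amount requires withdrawal from the study. When this is found at Visit 2, it forfeits the period-2 VAS and OSDI and that subject's contrast.

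The main cost is precision, about 4 percentage points of power (79.2% to 83.0%) for five pairs kept, at SD 25, Δ = 10 and ρ = 0.5.

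Bias is conditional. It was material only when non-compliance was related to comfort and differed by drop, and either incomplete pairs were discarded (7.14 for a true 5) or the non-compliant period's own VAS was also lost (10.36 with the likelihood, 9.29 with complete pairs). With the current-visit VAS kept and all available data used, estimates were 4.91 to 5.08 in every mechanism tried. The plan does not commit to that analysis, so the protection is not assured.

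A reader might also infer that ITT collapses into per-protocol. That is not shown: per-protocol requires every visit completed, while ITT requires one observation.

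The mechanisms and rates are assumptions, and period effects were not simulated. For an exploratory pilot this is a cheap improvement, not a flaw that invalidates the comparison.

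**What to change.** Reconcile Section 8.2 with Sections 14.3, 14.5 and 14.9:

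1. In 8.2, separate withdrawal from outcome collection from decisions about the drop. Non-compliance with the usage schedule alone is recorded as a deviation and does not by itself end collection of VAS and OSDI at the remaining visits. Say what counts as non-compliance for this purpose.
2. Handle such deviations through the per-protocol set that already exists.
3. In 14.5 and 14.9, name the primary population. State that the model uses all available period outcomes, including incomplete pairs, and state the missing-data assumption that this rests on.

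Whether a subject stops or continues a drop, or receives the second one, stays with the existing clinical text; nothing is proposed on that.

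The cost is protocol and analysis wording, plus remaining visits for a few subjects. The downside is that some outcomes will reflect partial use, which the per-protocol analysis addresses. Outcomes that are never collected cannot be recovered at the analysis stage.

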## **9. PRE-STUDY AND CONCOMITANT INTERVENTION/MEDICATION**

Concomitant medications will be documented during screening and updated during the study. Disallowed medications for this study include: Current habitual use of Prescription Only Medicines for dry eye or ocular discomfort, ocular steroids, or any medication (RX or OTC) that would interfere with the clinical study (at the discretion of the investigator).

Concomitant therapies that are disallowed include: Current habitual use of Prescription Only Medicines for dry eye or ocular discomfort, ocular steroids, or any medication (RX or OTC) that would interfere with the clinical study (at the discretion of the investigator).

## **10. DEVIATIONS FROM THE PROTOCOL**

Investigator will notify study sponsor upon identification of a protocol deviation. Major protocol deviations must be reported to the sponsor within 24 hours after discovery of the protocol deviation. The Investigator will report deviations per IRB/IEC requirements. All deviations will be tracked and corrective actions implemented as appropriate.

If it becomes necessary for the Investigator to implement a deviation to eliminate an immediate hazard to the trial subject, the Investigator may implement the deviation immediately without notification to the sponsor. Within 24 hours after the implemented deviation, the Investigator must notify and provide the rationale to the Sponsor and, as required, the IEC/IRB.

## **11. STUDY TERMINATION**

The occurrence of one or more Unanticipated Serious Adverse Device Effect (USADE), or any SAE where the relationship to study agent cannot be ruled out, may result in stopping further dispensing of test article. In the event of a USADE or SAE, the Sponsor may

unmask the treatment regimen for the subject(s) and will discuss this with the Investigator before any further subjects are enrolled.

The Sponsor will determine when a study will be stopped. The Principal Investigator always has the discretion to initiate stopping the study based on patient safety or if information indicates the study's results are compromised.

JJV reserves the right to terminate the study at any time for any reason. Additionally, the IEC/IRB reserves the right to terminate the study if an unreasonable risk is determined. The study can be terminated by the Principal Investigator at the individual clinical site due to specific clinical observations, if in their opinion, after a discussion with JJV, it is determined that it would be unwise to continue at the clinical site.

JJV (and the IEC/IRB and DMC, if applicable) will evaluate all adverse events. If it is determined that an adverse event presents an unreasonable risk, the investigation, or that part of the investigation presenting the risk, will be terminated, as soon as possible.

Should the study be terminated (either prematurely or as scheduled), the Investigator will notify the IEC/IRB and Regulatory Authority as required by local regulatory requirements.

